6.4.2.3. Analysis of exploratory Health-Related Quality of Life (HRQoL) endpoints

HRQoL questionnaires include Short-Form 36 Health Survey (SF-36), Work Productivity and Activity Impairment questionnaire (WPAI), EuroQoL (health-related quality of life questionnaire) (EQ-5D), and inflammatory bowel disease questionnaire (IBDQ).

HRQoLs will be collected at baseline, Week 10, Week 26, and Week 58.

SF-36

The SF-36 is a health related quality of life instrument consisting of 36 questions belonging to 8 domains in 2 components and covers a 4-week recall period:

- Physical well-being, 4 domains: physical functioning (10 items), role physical (4 items), bodily pain (2 items), and general health perceptions (5 items)
- Mental well-being, 4 domains: vitality (4 items), social functioning (2 items), role emotional (3 items), and mental health (5 items).

The remaining item (health transition) is not part of the above domains but is kept separately. These scales will be rescaled from 0 to 100 (converting the lowest possible score to 0 and the highest possible score to 100), with higher scores indicating a better quality of life. The SF-36 is not disease specific and has been validated in numerous health states.

The change from baseline at Week 10 for Cohort A and B Induction Studies and the change from re-baseline at Weeks 26 and 58 for Maintenance Study in each of the 8 domains and each of the 2 components in SF-36 will be analyzed using an ANCOVA model. The model will include treatment, stratification factors and baseline/re-baseline score as covariates. LOCF approach will be used to impute missing values. Estimated means of treatment effects and estimated differences in treatment effects between each filgotinib treatment group and the placebo group will be presented with 95% CIs and nominal p-values.

Descriptive statistics will be used to summarize the absolute values and change-from baseline (or re-baseline) values for each domain as well as each component by treatment group and analysis visit.

WPAI

The WPAI is a designed to measure the effect of general health and symptom severity on work productivity and regular activities during the past seven days.

The questionnaire consists of 6 questions:

- Q1: currently employed,
- Q2: work time missed due to UC,
- Q3: work time missed due to other reasons,
- Q4: hours actually worked,
- Q5: degree UC affected productivity while working (0-10 VAS; with 0 indicating no effect and 10 indicating UC completely prevented the subject from working),
- Q6: degree UC affected productivity in regular unpaid activities (0-10 VAS; with 0 indicating no effect and 10 indicating UC completely prevented the subject's daily activities).

WPAI outcomes are expressed as impairment percentages, with higher numbers indicating greater impairment and less productivity, that is, worse outcomes, as the following domains:

- The percentage of work time missed (absenteeism) due to UC: $100 \times Q2 / (Q2 + Q4)$
- The percentage of impairment while working (presenteeism) due to UC: $100 \times Q5 / 10$
- The percentage of overall work impairment (work productivity loss) due to UC: $100 \times \{ Q2 / (Q2 + Q4) + [(1 - Q2 / (Q2 + Q4)) \times (Q5 / 10)] \}$
- The percentage of activity impairment due to UC: $100 \times Q6 / 10$.

Summary statistics of the absolute and change from baseline (or re-baseline) scores for each of the four domains will be displayed by treatment and visit.

The change from baseline at Week 10 for Cohort A and B Induction Studies and the change from re-baseline at Weeks 26 and 58 for Maintenance Study will be analyzed using similar ANCOVA models as for SF-36.

EQ-5D

The EQ-5D is a standardized instrument developed by the EuroQol Group as a measure of health-related quality of life that can be used in a wide range of health conditions and treatments.

The EQ-5D consists of 2 components: a descriptive system of the subject's health and a rating of his or her current health state using a 0 to 100 VAS. The descriptive system comprises the following 5 dimensions: mobility, self-care, usual activities, pain/discomfort, and anxiety/depression. Each dimension with 5 levels of severity is used for our study: no problems, slight problems, moderate problems, severe problems, and extreme problems. The VAS records the subject's self-rated health on a vertical VAS in which the endpoints are labeled "best imaginable health state" on the top and "worst imaginable health state" on the bottom. Higher EQ VAS indicates better health.

The EQ-5D data will be summarized by treatment group and visit as the following:

- A health profile: summary statistics will be provided, including number of patients and proportions of categorical responses for the 5 dimensions (mobility, self-care, usual activity, pain/discomfort, and anxiety/depression)
- A self-perceived current health score: calculated from patient level EQ VAS responses (continuous variable). The mean, SD, min, median, and max scores will be provided.

The change from baseline at Week 10 for Cohort A and B Induction Studies and the change from re-baseline at Weeks 26 and 58 for Maintenance Study will be analyzed using similar ANCOVA models as for SF-36.

IBDQ

This disease-specific questionnaire comprises 32 questions divided into four health subscales: bowel symptoms (10 questions); systemic symptoms, including sleep disorders and fatigue (5 questions); emotional function such as depression, aggression, and irritation (12 questions); and social function, meaning the ability to participate in social activities and to work (5 questions).

Summary statistics of the absolute and change from baseline (or re-baseline) scores for IBDQ total score and each subscale score will be displayed by treatment and visit.

The change from baseline at Week 10 for Cohort A and B Induction Studies and the change from re-baseline at Weeks 26 and 58 for Maintenance Study will be analyzed using similar ANCOVA models as for SF-36.

6.5. Interim Efficacy Analyses

6.5.1. DMC Futility Analysis

After the initial DMC meeting, the second DMC meeting will include an interim futility analysis for each Induction Study after approximately 175 subjects reach Week 10 or discontinue from study. The futility analysis will be conducted to evaluate endoscopic efficacy. Overall safety will be evaluated at this timepoint as well. The proportion of subjects who achieve an endoscopic subscore of 0 or 1 for each treatment group will be evaluated. The DMC may recommend termination of a filgotinib dose group in the Induction Study that is being evaluated if the observed proportion of subjects who achieve endoscopic response in the filgotinib group is lower than that in the placebo group. If both filgotinib dose groups meet the futility criteria, the DMC may recommend stopping the study (ie, Cohort A Induction Study [biologic naïve], Cohort B Induction Study [treatment experienced], or both).

Should the DMC recommend that the study be modified, a Gilead employee (the sponsor representative, as defined in the DMC charter) may be provided with unblinded study data in order to make a decision about study conduct. Unblinding of specific Gilead personnel will be documented per the appropriate standard operation procedures (SOP).

6.5.2. DMC Cohorts A and B End-of-Induction Analysis

After all subjects from Cohorts A and B have completed the Week 10 visit or have terminated prior to Week 10 and corresponding data entry is complete, an End of Induction safety and efficacy analysis will be performed, including cumulative safety analysis and analysis on primary endpoint. Gilead Sciences, Inc.'s (Gilead) blinded statistical programmers will provide unblinded external statistician, who is independent of Gilead and not a member of Gilead's Study Management Team, with the datasets and programs necessary to complete the analysis. The unblinded external statistician will apply the unblinded treatment codes to the datasets and generate the unblinded analysis results.

Both cohorts will be examined independently by DMC:

- Taking into account data in Cohort A and Cohort B, if both dosing groups (200 mg and 100 mg) in both cohorts (independently examined) fail to reach statistical significance compared to placebo on EBS remission, the DMC may recommend overall study discontinuation.
- If the condition above is not met, the DMC may recommend that the study continue without modification.

6.6. Change from Protocol-Specified Efficacy Analyses

Protocol amendment 5 (02 April 2019) Section 8.11, described that a review of the results of all primary and key secondary endpoints of Cohort A and B Induction Studies would be performed by a Gilead executive team in parallel with the DMC's review of the end of induction analysis.

However, this review by a Gilead executive team was not performed due to concerns raised by the Voluntary Harmonization Procedure (VHP) during protocol review. No Gilead executive team member or GS-US-418-3898 study team member had access to any unblinded study results prior to study completion and database finalization/lock.

EBS remission (alternative definition), endoscopic response, MCS response, changes from baseline in MCS and partial MCS at Weeks 10 and 58 are included as exploratory endpoints for Cohort A Induction Study, Cohort B Induction Study, and Maintenance Study. The analyses on these endpoints are also included as exploratory analyses.

7. SAFETY ANALYSES

7.1. Adverse Events and Deaths

7.1.1. Adverse Event Dictionary

Clinical and laboratory AEs will be coded using the current version of MedDRA. System organ class (SOC), high-level group term (HLGT), high-level term (HLT), preferred term (PT), and lower-level term (LLT) will be provided in the AE dataset.

7.1.2. Adverse Event Severity

Adverse events are graded by the investigator as Grade 1, 2, 3, 4, or 5 according to toxicity criteria specified in the protocol. The severity grade of events for which the investigator did not record severity will be categorized as “missing” for tabular summaries and data listings. The missing category will be listed last in summary presentation.

7.1.3. Relationship of Adverse Events to Study Drug

Related AEs are those for which the investigator selected “Related” on the AE case report form (CRF) to the question of “Related to Study Treatment.” Relatedness will always reflect the investigator assessment of causality rather than the sponsor’s. Events for which the investigator did not record relationship to study drug will be considered related to study drug for summary purposes. However, by-subject data listings will show the relationship as missing.

7.1.4. Serious Adverse Events

Serious adverse events (SAEs) will be identified and captured as SAEs if AEs met the definitions of SAE specified in the study protocol. Serious adverse events captured and stored in the clinical database will be reconciled with the SAE database from the Gilead Pharmacovigilance & Epidemiology Department before data finalization.

7.1.5. Treatment-Emergent Adverse Events

7.1.5.1. Definition of Treatment-Emergent Adverse Events

Treatment-emergent adverse events (TEAEs) are defined as 1 or both of the following:

Induction Studies (Cohort A Induction Study and Cohort B Induction Study)

- Any AEs with an onset date on or after the study drug start date for each Induction Study (Day 1) and:

No later than 30 days after the last dosing date of Induction Study, for subjects who did not take any study treatment from Maintenance Study, or

Before the first dosing date of Maintenance Study, for subjects who took any study treatment in Maintenance Study

- Any AEs leading to premature discontinuation of Induction study drug

Maintenance Study

- Any AEs with an onset date on or after the study drug start date for the Maintenance Study and up to 30 days after last dosing date of Maintenance Study
- Any AEs leading to premature discontinuation of Maintenance study drug

Overall (Induction and Maintenance)

- Any AEs with an onset date on or after the study drug start date for the entire study and up to 30 days after last dosing date of either Induction Study or Maintenance Study, whichever is later
- Any AEs leading to premature discontinuation of either Induction or Maintenance study drug

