### 3.2. Study Design

These are combined Phase 2b/3, double-blind, randomized, placebo-controlled studies evaluating the efficacy and safety of filgotinib in the induction and maintenance of remission in subjects with moderately to severely active UC. A schematic of this study is provided in Figure 3-1.

Figure 3-1. Study Schema

FIL = filgotinib; PBO = placebo; mg = milligram.

Non-responders are subjects who achieve neither EBS remission nor MCS response at Week 10

Subjects in the Maintenance Study that meet disease worsening criteria (see Section 3.6) will be offered open-label filgotinib.

This study includes:

- Screening (Days -30 to -1)
- Randomization (Day 1)
- Blinded Induction Studies (Day 1 to Week 11)
  - Cohorts A and B Week 10 efficacy assessments
    - At Week 10, MCS to assess MCS response or EBS remission
  - Blinded Bridge Phase (Week 10 to 11): Dosing will continue in a blinded fashion through the end of Week 10 until re-randomization at Week 11
- Re-randomization (Week 11)
  - Subjects in Cohorts A and B who complete the Induction Study and achieve either EBS remission or MCS response at Week 10 will be re-randomized into the Maintenance Study at Week 11
  - Subjects who achieve neither EBS remission nor MCS response at Week 10 will have the option to enter a separate, Long-Term Extension (LTE) study (GS-US-418-3899)

- Blinded Maintenance Study (Weeks 11 to 58)
- Post-Treatment (PT) safety assessments:
  - Subjects who opt out of the LTE study (GS-US- 418-3899) will return 30 days after the last dose of study drug for PTx safety assessments
  - Subjects who complete all procedures per protocol, including the endoscopy, of the 58-week study will be offered the option to continue into the LTE study (GS-US-418-3899)
  - Subjects who are eligible and opt to participate in the LTE study (GS-US-418-3899) can continue into the study without PTx safety assessments

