### **Induction Studies (Cohorts A and B)**

All safety data collected on or after the first dose of study drug administration for each Induction Study (Day 1) up to:

- 30 days after last dose date, for subjects who prematurely discontinued study drug prior to or at Week 10 OR
- Week 10, for subjects who completed Week 10 dosing and continued on study drug will be summarized by treatment group according to the study drug received.

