### **Maintenance Study**

All safety data collected on or after the first dose of study drug administration for the Maintenance study (Week 11) up to 30 days after permanent discontinuation of study drug will be summarized by treatment group according to the study drug received.

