### **Induction Studies (Cohorts A and B)**

- Any AEs with an onset date of on or after the study drug start date for each Induction study (Day 1) and prior to:
  - 30 days after last dose date, for subjects who prematurely discontinued study drug prior to or at Week 10 OR

- Week 10, for subjects who completed Week 10 dosing and continued on study drug
- Any AEs leading to premature discontinuation of study drug prior to Week 10.

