3.2. Subject Grouping

For analyses based on the All Randomized Analysis Sets and FAS, subjects will be grouped according to the treatment to which they were randomized. For analyses based on the Safety Analysis Sets, PP Analysis Sets, and Biomarker Analysis Set, subjects will be grouped according to actual treatment received. The actual treatment received will differ from the randomized treatment only when their actual treatment differs from randomized treatment for the entire treatment duration.

For the PK Analysis Sets, subjects will be grouped according to the actual treatment they received.

For the summary of AEs and laboratory abnormalities using the Overall Safety Analysis Set, subjects will be grouped according to the actual treatment received across Induction and Maintenance studies, if applicable.

In general, all data will be summarized by treatment group for:

- Cohort A Induction Study
- Cohort B Induction Study
- Cohort A and B Induction Studies combined (not applicable to efficacy analysis)
- Maintenance Study

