7.1.5.2. Incomplete Dates

If the onset date of the AE is incomplete and the AE stop date is not prior to the first dosing date of study drug, then the month and year (or year alone if month is not recorded) of onset date determine whether an AE is treatment emergent. For first dosing date and last dosing date defined for the Induction Studies (Cohort A Induction Study and Cohort B Induction Study), Maintenance Study and Overall, please refer to Section 3.8.1. The event is considered treatment emergent if both of the following 2 criteria are met:

Induction Studies (Cohort A Induction Study and Cohort B Induction Study)

- The AE onset date is the same as or after the month and year (or year) of the first dosing date of study drug, and
- The AE onset date is the same as or before the month and year (or year) of the date corresponding to
 - 30 days after the last dosing date of Induction Study, for subjects who did not take any treatment from Maintenance, or
 - the day before the first dosing date of Maintenance Study, for subjects who took any study treatment in Maintenance Study

Maintenance Study

- The AE onset date is the same as or after the month and year (or year) of the first dosing date of Maintenance Study and
- The AE onset date is the same as or before the month and year (or year) of the date corresponding to 30 days after last dosing date of Maintenance Study

Overall (Induction and Maintenance)

- The AE onset date is the same as or after the month and year (or year) of the first dosing date of study drug, and
- The AE onset date is the same as or before the month and year (or year) of the date corresponding to 30 days after last dosing date of either Induction Study or Maintenance Study, whichever is later

An AE with completely missing onset and stop dates, or with the onset date missing and a stop date later than the first dosing date of study drug, will be considered to be treatment emergent. In addition, an AE with the onset date missing and an incomplete stop date with the same or later month and year (or year alone if month is not recorded) as the first dosing date of study drug will be considered treatment emergent.

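### No adverse-event or laboratory window in the SAP closes at the first extension-study dose, and adverse events are shown only as crude percentages although follow-up can differ by arm

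*SAP*

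**What the plan says.** **Adverse-event windows.** SAP 7.1.5.1 defines three.

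- Induction closes before the first Maintenance dose for subjects who took Maintenance drug. For everyone else the limit is "No later than 30 days after the last dosing date of Induction Study, for subjects who did not take any study treatment" in Maintenance.
- Maintenance and Overall run to 30 days after the last dose.
- The incomplete-date rule in SAP 7.1.5.2 repeats the Induction limit: "30 days after the last dosing date of Induction Study, for subjects who did not take any treatment from Maintenance".

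**Laboratory windows.** SAP 7.2, 7.2.2.1 and 7.2.2.2 use the same 30-day limit. None of these sections mentions the LTE.

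**Grouping.** SAP 3.2 reassigns a subject only in one case: "The actual treatment received will differ from the randomized treatment only when their actual treatment differs from randomized treatment for the entire treatment duration". For Overall tables, "subjects will be grouped according to the actual treatment received across Induction and Maintenance studies"; LTE drug is not mentioned.

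**Who can start LTE drug.** Protocol 3.4 offers open-label filgotinib in the LTE to Week 10 non-responders. Protocol 3.6 requires blinded drug to stop on disease worsening and offers the same route, except to subjects who need prohibited medication. Week 58 completers may continue in the LTE, but blinded.

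**Collection.** Protocol 7.3.1 requires all adverse events to be reported until 30 days after the last dose, with no LTE exception. Protocol 6.5 exempts LTE entrants from the post-treatment visit.

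**Summaries.** SAP 7.1.6.1 and 7.1.7 give numbers and percentages of subjects. Exposure is tabulated separately (SAP 4.2.1) and is not used as a denominator.

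**Protocol window.** Protocol 8.6 and 8.6.2 set the Induction limit by a different rule: "Week 10, for subjects who completed Week 10 dosing and continued on study drug", with the 30-day tail only for premature discontinuation. SAP 7.7 declares no deviation from the protocol's safety analyses.

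**The concern.** The SAP already accepts that a window should end when the next treatment starts, because it closes Induction at the first Maintenance dose. It does not apply that principle to the LTE. As written, an infection that starts on open-label filgotinib two weeks after a placebo subject's last blinded dose meets the definition of a treatment-emergent event on placebo.

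Two features make counted time depend on response, and so on arm if filgotinib works. In Induction the 30-day tail goes only to subjects who took no Maintenance drug, who are largely non-responders. In Maintenance, worsening forces blinded drug to stop. The two run in opposite directions: the placebo window is longer in Induction and shorter in Maintenance. A reader of crude percentages therefore cannot apply one mental correction to both. Safety and tolerability is a secondary objective of all three studies, and these tables are its main output.

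**Working it through.** **The plan's own figure.** The 55% response in SAP 1.3 gives 0.55 × (260 + 260) = 286 per dose, against about 285 stated, so it reproduces. It implies that 45% of filgotinib subjects are non-responders who may enter the LTE.

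**Assumptions not in the documents.** Placebo response is 25 to 45%, so r = 0.55 to 0.75 of placebo subjects may enter. LTE uptake, the gap L before the first LTE dose, the share c of LTE-drug events captured in this study's database, and Maintenance exit shares are also assumed.

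**Induction window length** (LTE entry straight after the last dose). Responders have about 77 days. Non-responders have 71 + 30 = 101 to 78 + 30 = 108 days.

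- Filgotinib: 0.55 × 77 + 0.45 × 101 = 87.8 days, or 91.0 with 108.
- Placebo: 0.45 × 77 + 0.55 × 101 = 90.2 days, up to 0.25 × 77 + 0.75 × 108 = 100.2.
- Placebo/filgotinib: 1.03 to 1.10. With the window closed at the first LTE dose: 0.98 to 1.00.
- With a 14-day gap and the cut: (77 + 0.55 × 14)/(77 + 0.45 × 14) = 84.7/83.3 = 1.02, up to 87.5/83.3 = 1.05.

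**Induction ratio of percentages** (rare event, true ratio 2, gap days at placebo risk, all non-responders entering the LTE):

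[77 × 2 + 0.45 × (L + c(30 − L) × 2)] / [77 + r × (L + c(30 − L) × 2)]

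| L = 14 | r = 0.55 | r = 0.75 |
|---|---|---|
| c = 0, or window cut | 160.3/84.7 = 1.89 | 160.3/87.5 = 1.83 |
| c = 0.5 | 167.5/93.5 = 1.79 | 167.5/99.5 = 1.68 |
| c = 1 | 174.7/102.3 = 1.71 | 174.7/111.5 = 1.57 |

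With no gap, full capture gives 181/110 = 1.65 to 181/122 = 1.48, and the cut restores 2.00. If only half of the non-responders enter the LTE and the rest have 30 off-drug days, full capture gives 1.62 to 1.75 and the cut 1.75 to 1.84 (L = 14).

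**Maintenance follow-up.** Day 78 to Day 407 is 329 days. If a share w leaves evenly over time, mean time on blinded drug is 329 × (1 − w/2). Adding 30 days for all:

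- 30% leaving on filgotinib v 40% on placebo: 309.65/293.2 = 1.06
- 20% v 40%: 326.1/293.2 = 1.11
- 30% v 60%: 309.65/260.3 = 1.19
- 20% v 60%: 326.1/260.3 = 1.25

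With the 30 days given to leavers only, the range is 1.05 to 1.22. At an equal true rate of 3 per 100 subject-years, 30% v 60% leaving gives 2.5% v 2.1%. With the cut and exposure-adjusted rates (L = 14), a true ratio of 2 shows as about 1.99.

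**SAP and protocol Induction windows side by side.** The protocol closes at Week 10 (Day 71) for subjects who continue. The SAP runs to the first Maintenance dose (about Day 78). In between, "Dosing will continue in a blinded fashion through the end of Week 10 until re-randomization at Week 11" (Protocol 3.2). The SAP wording covers those bridge days. It also gives the 30-day tail to Week 10 completers who take no Maintenance drug.

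**The case against.** The strongest objection is that the first part has an effect only if events starting on LTE drug enter this study's database. The LTE is a separate study and its entrants skip the post-treatment visit. That stands: at zero capture the cut changes nothing. But Protocol 7.3.1 makes no exception for LTE entrants, and Protocol 7.3.2 asks for serious events within 30 days even after the follow-up visit, so zero capture cannot be assumed either. For laboratory data capture is less likely, since the scheduled post-treatment sample falls away.

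Second, Protocol 8.6.2 itself specifies numbers and percentages, the tables are descriptive, and exposure is tabulated by arm. The by-subject listings of events and dosing let a reader find every onset after the last blinded dose. This stands and lowers the priority. The listings bound the problem, but they do not separate off-drug days from open-label days, because no planned output gives the LTE first-dose date.

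Third, the sizes are small. A gap of 2.5% v 2.1% is less than one subject in arms of 190 and 95. In Induction the cut alone nearly equalises follow-up when non-responders enter the LTE promptly. Both stand, and rate tables therefore matter mainly in Maintenance.

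Fourth, the SAP revision log refers to a separate integrated safety SAP, which may plan rates. It is not available here and would not change this SAP's definitions.

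Fifth, the protocol's Week 10 limit can be read as the end of Week 10, close to the SAP's limit. That is a fair reading of 8.6, though 8.6.2 says prior to Week 10. Either way the rule for who gets the 30-day tail differs.

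**Conclusion.** The point holds on the text. No adverse-event or laboratory window closes at the first LTE dose, the grouping rules do not move such events, and adverse events are reported only as crude percentages.

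In Induction, the missing cut ranges from no effect to a modest pull toward no difference for an event that filgotinib makes more frequent: 1.57 to 1.71 at full capture, against 1.83 to 1.89 with the cut, for a true ratio of 2.0. In Maintenance, unequal follow-up could inflate a crude ratio by about 1.05 to 1.25. All these sizes rest on assumed uptake, gap, capture, placebo response and exit shares.

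Three stronger readings are not supported.

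- A reader might infer that open-label events will be counted under placebo. The documents make this possible and do not state capture.
- A reader might infer that Induction needs rate tables as much as Maintenance. With prompt LTE entry the cut leaves follow-up within about 2%. A 14-day gap leaves placebo 2 to 5% longer.
- A reader might infer that the undeclared Induction window biases a result. It sensibly covers the bridge week, and the only fault shown is the missing entry in SAP 7.7.

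No sample size, power or alpha figure is affected. Priority is low to modest.

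**What to change.** 1. In SAP 7.1.5.1, 7.1.5.2, 7.2, 7.2.2.1 and 7.2.2.2, end each window at the earlier of 30 days after the last dose and the day before the first LTE dose, and keep the existing limits where a window already closes at the first Maintenance dose. Changing the adverse-event sections alone would leave laboratory tables covering different days for the same subjects. Keep the uncut version as a sensitivity table.
2. Add exposure-adjusted incidence rates per 100 subject-years with 95% CI for treatment-emergent events, serious events and events of interest. Do this primarily for Maintenance; Induction is optional once the cut is made. Numerator and denominator must cover the same days, from first dose to the end of the cut window.
3. Record in SAP 7.7 that the Induction window is defined by Maintenance dosing and not by the Week 10 rule of Protocol 8.6 and 8.6.2. This is a documentary correction only.

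The cost is merging LTE first-dose dates from another study's database, a few SAP clauses, the sensitivity tables and a set of rate tables. Some delayed effects of blinded drug, mostly in non-responders, would move from the main table to the sensitivity table.
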